
sequencing results as a composite reference standard.
 
1.2 Estimate the diagnostic accuracy of the Xpert MTB/XDR assay for fluoroquinolone resistance detection, for a clinically diverse set of TB samples, with phenotypic DST and gyrA and gyrB sequencing results as a composite reference standard.
 
1.3 Estimate the diagnostic accuracy of the Xpert MTB/XDR assay for second-line injectable resistance detection, for a clinically diverse set of TB samples, with phenotypic DST and rrs and eis sequencing results as a composite reference standard.
		
1.2 Sensitivity and specificity estimates for fluoroquinolone resistance detection
 
1.3 Sensitivity and specificity estimates for second-line injectable resistance detection

1.4 Assess Xpert MTB/XDR operational aspects and ease of use, including Xpert MTB/XDR non-determinant rates.
	
Completion of laboratory CRFs for all samples and completion of user-appraisal questionnaires by at least two operators per site at two different timepoints (after training and after study completion)
	
1.4 Assessment of Xpert MTB/XDR operational aspects and ease of use

Secondary		

2.1 Assess additional Xpert MTB/XDR performance characteristics:
 
 ○ Direct performance versus performance on cultured samples ○ Performance between sites ○ Performance by smear result ○ Performance by gene target ○ Performance compared to Hain MTBDR_{plus/sl} ○ Performance by patient HIV status ○ Performance by patient pre-treatment status ○ Performance as reflex test to Ultra or MTB/RIF assay 	
Smear, culture, NGS, MTBDR_{plus}, MTBDR_{sl} and two Xpert MTB/XDR results (direct from sputum and from cultured strain) for each clinical sample tested
	
2.1 Assessment of additional Xpert MTB/XDR performance characteristics

3 Study Design

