5.3.2 Index Test

The Xpert MTB/XDR assay detects Mtb mutations associated with INH, ETH and second-line drug resistance direct from sputum. In line with this intended use, clinical samples will be directly tested by the Xpert MTB/XDR assay. However, the assay will also be used to test the culture isolate. This additional Xpert MTB/XDR assay testing will allow for a comparison of performance and non-determinant rates between testing directly from the sample and testing from the culture isolate. It will also support resolution of potential discordant LPA and NGS results from the initial Xpert MTB/XDR test result, as these tests will also be performed from the culture isolate (discordance may arise as a result of infections with a mix of different strains, with only one strain being grown out in culture). Furthermore, as all assays will be performed on the same culture, there is also no risk of any assay being tested on a different quality sample.

Review bias will be avoided in this study as the index test requires no manual interpretation by the operator. All results are automatically generated by the GeneXpert instrument and will be directly recorded by the operator on the laboratory case report form (CRF).

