6.1.2 Study Workflow

Study flow is shown in Figure 1. All available Xpert MTB/RIF TB-positive samples will be tested in this study (i.e. consecutive patient samples) until sample size targets are met. All molecular assays will be performed in accordance with SOPs provided by the manufacturers. Specimen handling and processing by routine tests will be carried out according to NTP local policies and standards.

Samples will first be tested by Xpert MTB/RIF or Ultra, as part of routine diagnostic procedures. This Xpert MTB/RIF step will act as a screening tool for trial enrolment. Participants testing positive for MTB by Xpert MTB/RIF will be asked to volunteer for the Xpert MTB/XDR trial. This (testing of specimens from TB-positive samples) is in line with the intended use of the XDR assay as an add-on test to the Xpert MTB/RIF assay.

[figure not shown]
A staged enrolment will proceed: Stage 1 will enrol 360 MTB-positive participants, irrespective of RIF resistance/sensitivity. Once enrolment is complete, Stage 2 will enrol 400 MTB-positive RIF-resistant participants (see section 9.1 and Appendix 4: Sample Requirement to Achieve Target Sample Size). This staging is designed to better evaluate Xpert MTB/XDR sensitivity for second-line resistance detection.

In order to efficiently assess the diagnostic performance of the Xpert MTB/XDR assay, participants will be asked to provide ≥ 3 ml of sputum (either a single sputum or two consecutively collected and pooled sputa). Samples will be homogenized and split for testing.

The Xpert MTB/XDR assay and acid-fast bacilli smear will be performed on the direct sample. 2ml of sputum will be decontaminated and used for MGIT and LJ culture.

Following direct testing, phenotypic MGIT DST will be performed for all culture-positive samples for INH, RIF, fluoroquinolone (moxifloxacin and levofloxacin), AMK, ETH (ethionamide), KAN and CAP. Cultured samples will also undergo subsequent molecular testing by LPA and targeted NGS of relevant gene regions (*katG*, *inhA*, *fabG1*, *ahpC*, *gyrA*, *gyrB*, *rrs*, and *eis*) and another Xpert MTB/XDR assay. NGS will be performed from the culture isolate to obtain sequencing reads of high quality.

Figure 1. Phase II sample flow

≥ 3ml of sputum is required for the trial. This can be achieved through an individual sputum or pooling of serially collected sputa, homogenized with glass beads.

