9.2.3 Additional Characteristics Assessed

Secondary analyses will investigate assay diagnostic performance between important subgroups, including: Xpert MTB/XDR direct versus indirect performance (on direct versus cultured samples), performance between sites, by smear result, by gene target, performance compared to Hain MTBDR*plus* and MTBDR*sl* assays, performance by reflex test to Xpert MTB/RIF or Ultra result, and performance by patient HIV and pre-treatment status. Detailed definitions for diagnostic test results are given in Appendix 5: Definitions of Diagnostic Test Results.

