9.2.4 Efficacy Analyses

Endpoint	Statistical Analysis Methods
Primary	
 • Sensitivity • Specificity • Data summaries
Secondary	
 • Chi-squared • Sensitivity • Specificity • Positive Predictive Value • Negative Predictive Value

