4.3 Analysis of the secondary outcome(s)

Outcome 2.1

Direct performance versus performance on cultured samples:

- Estimates of diagnostic performance for each drug split by specimen type used for Xpert MTB/XDR (sputum or culture)

Performance between sites:

- Estimates of diagnostic performance for each individual site (India-NITRD, India-Hinduja, Moldova, and South Africa)

Performance by smear result:

- Estimates of diagnostic performance by smear gradation (smear negative, scanty, +1, +2, +3)

Performance by gene target

- Count of the number of times resistance was detected by the assay when a mutation was present in the gene region (NGS) for each gene target (*katG*, *inhA*, *ahpC*, *fabG1*, *gyrA*, *gyrB*, *rrs*, *eis*)

Performance compared to Hain MTBDR*plus/sl*

- Estimates of diagnostic performance for INH by Xpert MTB/XDR vs. Hain MTBDR*plus*
- Estimates of diagnostic performance for ETH by Xpert MTB/XDR vs. Hain MTBDR*plus*
- Estimates of diagnostic performance for FQ by Xpert MTB/XDR vs. Hain MTBDR*sl*
- Estimates of diagnostic performance for AMK/KAN/CAP by Xpert MTB/XDR vs. Hain MTBDR*sl*

Performance by patient HIV status:

- Estimates of diagnostic performance by HIV status (positive and negative)

Performance by patient pre-treatment status:

- Estimates of diagnostic performance by patient report of previous treatment for TB (yes and not)

Performance as reflex test to Ultra or MTB/RIF assay

- Estimates of diagnostic performance for each drug split by which test was used upfront (Ultra or MTB/RIF)

5 Baseline descriptive statistics

Descriptive statistics tables will be generated to summarize the characteristics of the participants. The number of participants included and excluded will be reported. Among the included participants, the information will be broken down by site, gender, and age group.

Results will be reported either in absolute numbers (e.g. number of subjects in a group) or summarized by mean, median, standard deviation, minimum, maximum and quartiles.

6 Planned interim analyses

Once 200 clinical samples have been tested by Xpert MTB/XDR both directly on the clinical sample and on the culture isolate, and have returned NGS results for all drugs tested, an interim analysis will be conducted. The diagnostic sensitivity and specificity of the Xpert MTB/XDR assay will be estimated against NGS for each drug evaluated, including for important sub-groups as detailed in Table 2.

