The results will serve as an early indicator of Xpert MTB/XDR accuracy in the clinical trial. If performance estimates fall outside of the presented confidence intervals for resistance detection (Table 2), the Data Monitoring Committee (DMC) will review all data for accuracy and consistency. Additionally, the sponsor may conduct a monitoring visit to one or more sites to ensure adherence to SOPs and effective data management.

7 Additional sub-group analyses

Subgroups analyses, and definitions of subgroups, are described in section 4.3. No additional subgroup analyses will be performed.

8 Multiple comparisons/multiplicity adjustments

No multiple testing of statistical hypotheses is going to be performed.

9 Exploratory analyses

No exploratory analyses will be performed.

10 Sample size

To achieve the targeted precision for accuracy estimates, it is estimated that 760 samples will need to be tested for this study, with a final 284 MTB-positive and an additional 316 RIF-resistant samples tested by Xpert MTB/XDR and all reference standards and comparators, i.e. a total of 600 specimen results available for analysis. The desired precision for the accuracy estimates was chosen to achieve high confidence in the estimates for Xpert MTB/XDR resistance detection when considering evidence from both the 'external laboratory validation' (phase I) and the clinical trial (phase II). The sample size is detailed below in Table 2.

		n	Point estimate (95%CI) *	Total width of CI *
INH	Sensitivity	395	90% (86, 93)	7%
	Specificity	205	98% (95, 99)	4%
FQs	Sensitivity	93	90% (82, 95)	13%
	Specificity	507	98% (96, 99)	3%
AMK	Sensitivity	34	90% (74, 97)	23%
	Specificity	566	98% (96, 99)	3%
KAN	Sensitivity	71	90% (80, 96)	16%
	Specificity	529	98% (96, 99)	3%
CAP	Sensitivity	34	90% (74, 97)	23%
	Specificity	566	98% (96, 99)	3%

Table 2 Sample size

* 95%CI based on Wilson's score method (as recommended by Newcombe et al. as well as CLSI/FDA) using continuity correction.

11 Minimization of error and bias

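### Direct v culture Xpert and Xpert v LPA are matched within sample, but neither the protocol nor the SAP plans a paired analysis of them

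*Protocol*

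**What the plan says.** **The data are paired.** For objective 2.1, the table in protocol section 2 collects, besides smear, culture, NGS and both Hain assays, "two Xpert MTB/XDR results (direct from sputum and from cultured strain) for each clinical sample tested". Protocol 6.1.2 adds: "Cultured samples will also undergo subsequent molecular testing by LPA and targeted NGS of relevant gene regions", followed by a second Xpert MTB/XDR run. Protocol 5.3.2 presents it as an advantage that there is no difference in sample quality, "as all assays will be performed on the same culture".

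**The protocol's analysis.** Section 9.2.3 opens with "Secondary analyses will investigate assay diagnostic performance between important subgroups". It then puts direct v indirect testing and the Hain comparison in one list with site, smear, HIV status, pre-treatment status and the upfront Xpert test. Section 9.2.4 gives the methods for all of these as "Chi-squared • Sensitivity • Specificity • Positive Predictive Value • Negative Predictive Value".

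**The SAP's analysis.** For direct v culture, SAP 4.3 plans "Estimates of diagnostic performance for each drug split by specimen type used for Xpert MTB/XDR (sputum or culture". For the LPA comparison its first item is "Estimates of diagnostic performance for INH by Xpert MTB/XDR vs. Hain" MTBDRplus, with similar lines for the other drugs. The only interval defined (SAP 4.1) is the Wilson interval for a single proportion. No test is named anywhere in the SAP, and section 8 states: "No multiple testing of statistical hypotheses is going to be performed".

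**The concern.** When two tests are run on the same samples and judged against the same reference result, the information about their difference lies in the discordant samples, those that one test calls correctly and the other does not. A method for independent groups ignores this. If results are positively correlated within a sample, as is likely for assays that read similar gene regions in one patient's specimen, it overstates the uncertainty of the difference.

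Protocol 3.2 gives direct v indirect testing and the comparison with LPA as things the study will assess, and protocol 1.1 says the evidence is to inform policy. A real loss of sensitivity on sputum, or a real difference from LPA, could be reported as no clear difference although the data already collected would show it. The risk is a missed difference. With positive correlation the error does not create false claims of a difference.

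**Working it through.** **1. The plan's own figures.** Table 2 (protocol 9.1, SAP section 10) uses the continuity-corrected Wilson interval. With q = 1 − p and z = 1.96:

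lower = [2np + z² − 1 − z√(z² − 2 − 1/n + 4p(nq + 1))] / [2(n + z²)]

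upper = [2np + z² + 1 + z√(z² + 2 − 1/n + 4p(nq − 1))] / [2(n + z²)]

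At p = 0.90:
- INH, n = 395: 86.5 to 92.7 (printed 86, 93; the lower limit is 86.50, a rounding matter)
- FQ, n = 93: 81.6 to 95.0 (printed 82, 95)
- KAN, n = 71: 80.0 to 95.5 (printed 80, 96)
- AMK/CAP, n = 34: 73.7 to 97.1 (printed 74, 97)

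The table reproduces. Each interval describes one test's proportion, so pairing does not alter it. No figure is given for any difference between tests.

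**2. Inputs for the illustration.** From the documents: n = 395 reference-resistant for INH and a sensitivity near 90%. Assumed: 355 detected by one test (355/395 = 89.9%) and 367 by the other (367/395 = 92.9%), a difference of 12/395 = 3.0 points. The discordant split is also assumed, so it is varied.

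**3. Treated as independent.** Half-width = 1.96 × √(0.8987 × 0.1013/395 + 0.9291 × 0.0709/395) = 1.96 × 0.01993 = 3.9 points. Pearson chi-squared on 355/40 v 367/28 gives p = 0.13 (0.16 with continuity correction). The two separate Wilson intervals without correction, 86.5 to 92.5 and 89.9 to 95.1, overlap.

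**4. Treated as paired.** Let b and c be the samples detected by only the first and only the second test. Half-width = 1.96 × √(b + c − (c − b)²/n) / n. For b = 4 and c = 16: √(20 − 144/395) = 4.431; 4.431/395 = 0.01122; × 1.96 = 2.2 points. With the same margins and other splits:

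| b v c | Within-sample correlation | Paired half-width (points) | Exact McNemar p |
|---|---|---|---|
| 4 v 16 | 0.69 | 2.2 | 0.012 |
| 8 v 20 | 0.56 | 2.6 | 0.036 |
| 12 v 24 | 0.43 | 3.0 | 0.065 |
| 16 v 28 | 0.30 | 3.3 | 0.096 |
| 25 v 37 | 0.01 | 3.9 | 0.16 |

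**5. Both tests at 90%.** The unpaired half-width is 1.96 × √(2pq/n). The paired one is that figure times √(1 − ρ), where ρ is the within-sample correlation. The unpaired interval is therefore too wide by 1/√(1 − ρ): 1.2 times at ρ = 0.3 and 2.2 times at ρ = 0.8. At ρ = 0.7 the half-widths, unpaired v paired, are 4.2 v 2.3 points for INH, 8.6 v 4.7 for FQ and 14.3 v 7.8 for AMK/CAP.

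**6. Error rate and power.** In a simulation of paired results (n = 395, ρ = 0.7, nominal two-sided 5%, 200,000 replicates), an unpaired Pearson test has a true type I error of 0.04%, against 5.3% for McNemar. For 90% v 87%, power is 12% with Pearson, 70% with asymptotic McNemar and 60% with its exact form.

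**The case against.** The strongest reply is that nothing wrong has been prescribed. Section 9.2.4 names chi-squared once, for a mixed list. Site, smear, HIV status, pre-treatment status and Ultra v MTB/RIF are independent groups, for which an ordinary chi-squared test is suitable, and McNemar's test is itself usually run as a chi-squared test. Protocol section 9 says that it gives key elements only, and the detailed plan, the SAP, runs no test. A reader might infer that the protocol orders an unpaired test for the paired comparisons. The text does not go that far; it is under-specified and does not match the SAP.

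A reader might also infer that the planned error bars are wrong. They are not: the Wilson intervals are for single proportions and each remains valid. No interval for a difference is planned, so none can be wrong.

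The size of the effect also depends on an assumed correlation. At the margins used above, exact McNemar p falls below 0.05 only in the two rows with correlation above 0.5, and near zero correlation pairing gains nothing. In the smallest group (AMK/CAP, n = 34), exact McNemar cannot reach two-sided 0.05 with fewer than six discordant pairs, even if all go one way: five give 2 × 0.5⁵ = 0.0625 and six give 0.031.

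All of this stands, and it limits the point. It does not fill the gap. The protocol groups two matched comparisons with independent subgroups, the SAP gives two columns of estimates with no difference, and SAP sections 7 and 9 rule out further subgroup or exploratory analyses that might have supplied one.

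**Conclusion.** The point holds as an omission in the secondary analysis. Direct v culture Xpert and Xpert v LPA are paired by design, and neither document states a paired difference, its interval or the discordant counts. Following either document as written gives a comparison that is at best as precise as the data allow and usually less so. In the INH illustration the 95% half-width is 3.9 points unpaired and 2.2 to 3.9 points paired, for correlations from about 0.7 down to 0. The margins, the discordant splits and the correlations are assumptions; only the group sizes and the 90% sensitivity come from the documents.

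The documents do not support a claim that the plan's conclusions would flip from non-significant to significant. That happens only at the higher assumed correlations, and the SAP plans no test. The single-proportion Wilson intervals, the primary estimates and the sample size are unaffected.

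**What to change.** **SAP 4.3.** For direct v culture and for Xpert v LPA, take samples with valid results on both tests. For each drug, report the paired difference in sensitivity (reference-resistant samples) and in specificity (reference-sensitive samples) with a paired 95% interval, together with the discordant counts. State which Xpert result, sputum or isolate, is compared with LPA. LPA is run on the cultured sample, and protocol 9.2 lets the isolate result prevail in the primary analysis when the two Xpert results disagree, so the choice is not obvious.

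**Protocol 9.2.4.** Limit chi-squared or Fisher to independent groups: site, smear, HIV status, pre-treatment status, and Ultra v MTB/RIF. If a test is kept for the paired comparisons, name McNemar, exact when discordant pairs are few.

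**SAP section 8.** Reconcile it with whatever tests are kept. Six drugs, two comparisons and two reference strata could give 6 × 2 × 2 = 24 McNemar tests. Reporting differences with intervals and no tests would avoid this.

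**Cost.** A few lines of text, a small amount of extra analysis and no new data. The paired set is limited to culture-positive samples with both results, so its size should be reported for each drug.

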9.3 Planned Interim Analyses

Interim analyses for the phase II clinical trial will be led by the Trial Manager and conducted by the Trial Statistician. Preliminary data will be analysed once for every 200 clinical samples tested. Briefly, once 200 clinical samples have been tested by Xpert MTB/XDR both directly on the clinical sample and on the culture isolate and have returned NGS results for all drugs tested, an interim analysis will be conducted. The diagnostic sensitivity and specificity of the Xpert MTB/XDR assay will be estimated against NGS for each drug evaluated, including for important sub-groups as detailed in section 2.

Data will be unmasked for this analysis, and results will serve as an early indicator of Xpert MTB/XDR accuracy in the clinical trial. If performance estimates fall outside of the presented confidence intervals for resistance detection (Table 2), the Data Monitoring Committee (DMC) will review all data for accuracy and consistency.

Additionally, the sponsor may conduct a monitoring visit to one or more sites to ensure adherence to SOPs and effective data management.

9.3.1 Data Monitoring Committee

The DMC for Phase II of the Xpert MTB/XDR evaluation will consist of the Head of TB Programme, Head of Clinical & Regulatory Affairs, Trial Manager, Data Manager, and the Data Entry Clerks at each study site. The head of the DMC will be the Data Manager, who will help to train site staff on the use of the database system and perform periodic data checks to ensure that data is collected, managed and reported clearly, securely and accurately throughout the project. The Data Entry Clerks at each site will perform first- and second-data entry and report any issues to the Trial Manager and Data Manager, who will work together with the Data Entry Clerks to resolve any data issues. The Head of Clinical & Regulatory Affairs will serve as an advisor to the DMC.

10 Regulatory and Ethical Considerations

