11.2 Data Management

For the clinical study, de-identified sample CRF data will consist of participant medical history, clinical examination, and prior laboratory testing results when available. All clinical CRF notes will be transferred to the eCRF by Data Entry Clerks.

All laboratory results (smear, culture, DST, molecular results) will be recorded by laboratory technicians directly on the laboratory CRF. All Xpert testing will generate electronic records of test results. All electronic results will be stored electronically on password-protected computers at the site. Data will also be transcribed into the CRF. LPA testing will generate results on paper test strips. These test strips will be interpreted by the operator and input into the laboratory CRF. All LPA test strips will be retained by the site as source documents. Laboratory CRFs will be transferred from paper CRFs to eCRFs by Data Entry Clerks at the sites and uploaded to the Openclinica study database. The OpenClinica Community v3.13 database is password controlled and restricted. FIND will ultimately be responsible for data management.

Electronic double-data entry must be conducted by two on-site Data Entry Clerks. Data entry training will be provided by FIND, either on site or remotely. Sites will use a password-protected web-based data-entry tool which has the advantage that study monitors will have continuous access to the electronic data. Electronic data will be backed up daily.

Where possible, first data entry will be done as soon as a result becomes available (real-time). Second data entry will only be done by study staff after all sample results

(culture, NGS, Xpert) are available. The Principal Investigator of each site will review all data entered for the site's samples.

Details relating to data entry procedures and timelines will be provided to the sites in a data management user manual.

Study monitors will conduct regular checks to see that all paper and electronic records are consistent and accurate. A priority during monitoring visits will be to ensure correctness of electronic data entries in comparison to source data.

Additional details relating to data entry procedures and timelines will be provided to the sites in the data management SOP.

12 Quality Management

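### Staff who enter data and resolve data issues take part in an unmasked, performance-triggered interim review, and no rule keeps corrections independent of index-reference agreement

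*Protocol*

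**What the plan says.** Protocol 9.3 has the Trial Manager lead the interim analysis and the Trial Statistician conduct it, once for every 200 samples, comparing Xpert MTB/XDR with NGS. On masking it says: "Data will be unmasked for this analysis, and results will serve as an early indicator of Xpert MTB/XDR accuracy in the clinical trial". If an estimate leaves its Table 2 interval, "the Data Monitoring Committee (DMC) will review all data for accuracy and consistency"; SAP section 6 uses the same words.

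Protocol 9.3.1 says that this committee "will consist of the Head of TB Programme, Head of Clinical & Regulatory Affairs, Trial Manager, Data Manager, and the Data Entry Clerks at each study" centre, with the Data Manager as head. It also describes their data duties: "The Data Entry Clerks at each site will perform first- and second-data entry and report any issues to the Trial Manager and Data Manager", and the two managers are the ones "who will work together with the Data Entry Clerks to resolve any data issues".

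SAP section 6 does not define the committee's membership and has no masking rule. Neither document restricts what the clerks see at the review, or requires concordant and discordant samples to be queried alike.

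**The concern.** A search for errors that is prompted by unexpected accuracy, and carried out by people who can see which pairs disagree, looks hardest at the discordant pairs. An entry error that makes index and reference disagree tends to be found and corrected. An error that happens to make them agree tends to stay. Each correction may be right in itself, yet the selection pushes sensitivity and specificity upward.

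Two routes are open: a wrongly transcribed call, or a wrongly transcribed field that decides exclusion from the primary analysis under Protocol 9.2.1 (an LJ count of 20 colonies or fewer, or MGIT time to positivity over 28 days). The estimates are meant to inform national and global policy, so it should be possible to show that corrections did not depend on concordance.

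**Working it through.** **1. Roles side by side** (Protocol 9.3, 9.3.1, 12.1)

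| Role | Part in the unmasked interim | Part in entry or correction |
|---|---|---|
| Trial Manager | Leads it; on the DMC | Data checks; resolves issues |
| Data Manager | Heads the DMC | Data checks; resolves issues |
| Site Data Entry Clerks | On the DMC | First and second entry; resolve issues |
| Trial Statistician | Conducts it | None stated |
| Head of TB Programme | On the DMC | None stated |
| Head of Clinical & Regulatory Affairs | On the DMC, as advisor | None stated |

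**2. The trigger limits reproduce.** The lower Wilson limit with continuity correction is [2np + z² − 1 − z√(z² − 2 − 1/n + 4p(nq + 1))] / [2(n + z²)], with q = 1 − p; the upper limit is the corresponding form. At p = 0.90:

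- INH, n = 395: 86.5 to 92.7 (Table 2: 86 to 93)
- FQ, n = 93: 81.6 to 95.0 (82 to 95)
- KAN, n = 71: 80.0 to 95.5 (80 to 96)
- AMK and CAP, n = 34: 73.7 to 97.1 (74 to 97)

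All are within 1 point. These limits describe the final denominators, but 9.3 applies them to interim estimates.

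**3. Resistant samples at the first look.** Stage 1 enrols first and is planned to give 284 analysable samples, so the first 200 are taken to be Stage 1. Appendix 4 rates × 200 give INH 0.29 × 200 = 58, FQ 0.05 × 200 = 10, AMK (and CAP) 0.02 × 200 = 4, KAN 0.01 × 200 = 2.

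**4. Chance that the trigger is met when true sensitivity is exactly 90%** (exact binomial, printed limits)

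| Drug | Resistant n | Results inside the interval | P(outside) |
|---|---|---|---|
| INH | 58 | 50 to 53 of 58 | 0.42 |
| FQ | 10 | 9 of 10 only: 10 × 0.9⁹ × 0.1 = 0.387 | 0.61 |
| AMK | 4 | 3 of 4 only: 4 × 0.9³ × 0.1 = 0.292 | 0.71 |
| KAN | 2 | none (0, 50 or 100% only) | 1.00 |

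If the resistant count also varies, as Binomial(200, rate), and a count of zero triggers nothing, the values are KAN 0.85, AMK 0.79 and FQ 0.57. The chance of any trigger is then at least 0.85 from KAN alone, with no independence assumption. Treating the four drugs as independent, with INH at its expected count, it is 1 − 0.151 × 0.213 × 0.429 × 0.579 = 0.99.

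If leaving the interval is read as falling below the lower limit only, the chances at the expected counts are INH 0.12, FQ 0.26, AMK 0.05 and KAN 0.19. With the four specificities (true value 98%) added and independence assumed, the chance of at least one is about 0.57. At 400 samples (284 Stage 1, 116 Stage 2) the figures are about 0.75 for either side and 0.18 for below only.

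**5. Discordant samples exposed at the first look.** Expected false negatives at 90% sensitivity are 10% of the counts in step 3: INH 5.8, FQ 1.0, AMK 0.4, KAN 0.2.

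**6. Weight of one changed call at the final denominators.** 1/34 = 2.9 points (AMK or CAP), 1/71 = 1.4 (KAN), 1/93 = 1.1 (FQ), 1/395 = 0.25 (INH). Excluding one false negative weighs about the same: for AMK, 31/33 − 31/34 = 93.9% − 91.2%, about 2.8 points.

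**The case against.** The case on the other side is substantial, and much of it stands.

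- **Clerks see concordance anyway.** Under Protocol 11.2, second entry takes place only after all of a sample's results are in. A reader might infer that committee membership is what lets clerks make later entries knowing which results disagree. The documents do not support that. The data flow already shows them, and reviewing earlier samples reveals at most a pattern, not which later samples will be discordant. A membership change alone would not blind the clerks.
- **Committee members do not read the tests.** Laboratory technicians record results on the CRF. For the line probe assays, "These test strips will be interpreted by the operator and input into the laboratory CRF". It is tempting to cite this as a route into the primary result, but these assays are comparators and are not in the composite reference standard (Protocol Table 1).
- **Safeguards exist.** Xpert and NGS records are electronic and retained. There is double entry, source data verification by monitors and investigator review, and changes to source data must be traceable (Protocol 11 to 12.1). An unsupported change would contradict the source. These controls show that a correction matches its source; they do not show whether the search for errors was even-handed. That gap is what remains.
- **The review is conditional, and access is partly inferred.** The DMC acts only if the trigger is met, the interim compares with NGS and not with the composite, and no text says that clerks receive sample-level concordance listings. Against this, the DMC is to review all data, nothing limits what its members see, and step 4 shows that the condition will probably be met. The Trial Manager leads the interim in any case.
- **The weights are not a bias.** A reader might pair the 2.9 points with the 400 of 600 results (67%) outstanding after the first look and infer a multi-point bias. Neither figure measures one. Known discordance applies to the samples already reviewed, and step 5 shows how few second-line false negatives those contain at the first look. No error or correction rate is given.

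**Conclusion.** The point holds as a weakness in procedure. The plan lets those who enter data and resolve data issues join an unmasked review triggered by performance, with no rule that separates corrections from concordance. The risk is confined to selective detection of genuine transcription or exclusion-field errors in discordant samples already reviewed. Its direction would be slightly upward for sensitivity and specificity. Its size cannot be estimated from the documents, and the existing controls limit it.

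That the review will probably happen at the first look (at least 0.85 if either side of the interval counts, about 0.57 if only the lower side does) rests on the Appendix 4 rates, true accuracy of 90% and 98%, and a first 200 drawn from Stage 1; the 0.57 also assumes independence. This is a cheap improvement worth making. It is not evidence that the primary estimates would be materially wrong.

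**What to change.** Amend three places together.

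- **Protocol 9.3:** the Trial Statistician conducts the interim and reports unmasked results only to the Head of TB Programme and the Head of Clinical & Regulatory Affairs. Change the statement that the Trial Manager leads the interim to match.
- **Protocol 9.3.1:** name one of these two as head of the interim review, since the Data Manager now heads the committee and the Head of Clinical & Regulatory Affairs is described as an advisor. The Trial Manager, Data Manager and clerks keep their ordinary data-checking duties.
- **Protocol 9.3 and SAP section 6:** any checks that follow go to sites as source-data queries on whole batches, concordant and discordant samples alike, without showing concordance and with every change logged. Repeat the membership in the SAP.

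The query rule is the essential part, because clerks will still see all of a sample's results at second entry. While these sections are open, reconcile the number of looks: Protocol 9.3 has one for every 200 samples, whereas SAP section 6 describes a single look at 200.

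The cost is wording only. The roles are already named and no sample size changes. The downside is somewhat slower query resolution, because sites check a batch and not just the flagged samples.
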